4.4.3. Laboratory

Blood and urine samples for the determination of clinical chemistry, hematology, and urinalysis laboratory variables described in [Table 10](#) will be measured.

Table 10 Laboratory Assessment

Lab Category	Lab tests
Hematology	hemoglobin, hematocrit, red blood cell count (RBC), white blood cell count (WBC), platelet counts, Absolute Reticulocyte Count, Reticulocyte %, Absolute Neutrophil Count, Neutrophils %, Absolute Lymphocyte Count, Lymphocytes %, Absolute Monocyte Count, Monocytes %, Absolute Basophil Count, Basophils %, Absolute Eosinophil Count, Eosinophils%
Chemistry	albumin, Alkaline Phosphatase (ALP), total bilirubin, direct bilirubin, indirect bilirubin, calcium, magnesium, chloride, creatinine, creatinine clearance rate, creatine phosphokinase, glucose, inorganic phosphorus, potassium, total protein, urine acid, glomerular filtration rate, Alanine Aminotransferase (ALT), Aspartate Aminotransferase (AST), Lactate Dehydrogenase (LDH), sodium, and Blood Urea Nitrogen (BUN)
Blood amylase and lipase	amylase, lipase
Fasting lipid panel	Total Cholesterol, High-density Lipoprotein, Low-density Lipoprotein, Triglycerides
Coagulation	Activated Partial thromboplastin time (aPTT), Prothrombin time (PT), International normalized ratio (INR)
Urinalysis	evaluation of glucose, protein, RBC, WBC, Ketone body, Urobilinogen
Virology	HIV, HBV (HBsAg, HBsAb, HBeAg, HBeAb, and HBcAb), HCV (HCV antibody), cytomegalovirus (CMV) (CMV antibody), CMV DNA, HBV DNA, HCV RNA

Lab Category	Lab tests
Other tests	HbA1C, pregnancy test, and other non-protocol specified tests (if any)

Change from baseline in laboratory test results to each assessment will be calculated for selected parameters. Data recorded by the laboratory will be converted to the International System of Units (SI) and all presentations will use SI units. Quantitative laboratory measurements reported as “< X”, i.e. below the lower limit of quantification (LLQ), or “> X”, i.e. above the upper limit of quantification (ULQ), will be converted to X for the purpose of quantitative summaries, but will be presented as recorded, i.e. as “< X” or “> X” in the listings.

Clinical laboratory results will be graded for selected parameters according to NCI CTCAE criteria, Version 5.0. Any assessment for which CTCAE toxicity grades are not available, will not be included in any analyses for which toxicity grades are required. Grade 0 is assigned to all laboratory values except missing values and not already assigned another grade. Missing values are considered missing.

Analysis of Abnormal Hepatic Laboratory Values

The following categories of abnormal hepatic laboratory values will be evaluated for any occurrence among all post baseline assessments.

- Aspartate aminotransferase (AST) > 3,5,8,10, and 20x ULN
- Alanine aminotransferase (ALT) > 3,5,8,10, and 20x ULN
- AST and/or ALT > 3,5,8,10, and 20x ULN
- Total bilirubin elevations > 1.5x, >=2x ULN
- ALP >1.5×, 2 × ULN
- AST and/or ALT > 3x ULN and (total bilirubin > 1.5×, >=2x ULN) [defined as at least one total bilirubin > 1.5×, >= 2x ULN within 14 days after ALT or AST > 3x ULN]
- Hy's Law criteria: AST and/or ALT > 3x ULN and total bilirubin \geq 2x ULN and ALP < 2x ULN [defined as at least one total bilirubin \geq 2x ULN and all ALP increase <2x ULN within 14 days after ALT or AST > 3x ULN]

Additionally, the minimum, and maximum values for each patient over the entire treatment period for each hematology, chemistry and coagulation laboratory parameter will also be derived. The change from baseline will also be calculated using these minimum and maximum values.

All laboratory results in SI units are presented in data listings.

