
Exploratory:
 
 To explore relationships between changes in frequency of genetic mutations, efficacy, PK, PD, and safety after HMPL-306 treatment To explore relationships between HMPL-306 PK drug exposure, target engagement (TE), 2-HG levels, and percentage inhibition To explore the influence of genetic abnormalities (other than IDH mutations) on safety, efficacy, PD, PK, and clinical response to HMPL-306 treatment 	
Exploratory:
 
 Changes from baseline in tumor markers, correlation with drug exposure, target engagement, and efficacy and safety outcomes

Brief Summary:
 
This is a phase 1, open-label, multicenter, single-arm study to evaluate safety, tolerability, PK, PD, and preliminary efficacy of HMPL-306 administered orally in treatment of patients with advanced relapsed, refractory, or resistant hematological malignancies that harbor IDH mutations (or co-mutations). The study consists of 2 parts: a dose escalation part (Part 1) and a dose expansion part (Part 2). The dose escalation part will determine the MTD/R2PD. The dose expansion part will administer the MTD/RP2D to:
 
 R/R AML patients who do not have standard therapeutic options available. The patients must have received at least 1 prior line of therapy with IDH inhibitors 	
Condition/Disease	Advanced relapsed, refractory, or resistant hematological malignancies that harbor IDH mutations
Study Duration	Approximately 36 months
Treatment Duration	28-day continuous dosing treatment cycle
Health Measurement/Observation	This study will determine the MTD and/or RP2D as well as safety assessments including DLTs, TEAEs, SAEs, ECGs, and clinical laboratory abnormalities. During the dose expansion part, patients will receive HMPL-306 daily at MTD/RP2D, for treatment cycles of 28 days until disease progression, death, intolerable toxicity, withdrawal of consent, lost to follow-up, conditions are met per Section 6.2.1, or end of study, whichever comes first.
Visit Frequency	PK week: every day for 1 week (Part 1 only) Cycle 1: every week (\pm 1 day, except D1)

	Cycle 2: every 2 weeks (± 1 day) Cycle 3 and onwards: day 1 (± 3 days) Treatment completion: within 7 days (± 3 days) after the last dose

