- If agreed upon by the investigators and the sponsor (eg, based on safety, PK, exposure, and TE and/or PD data from prior and current cohorts) that increasing the dose further may not yield additional benefit, the dose may stay at the current dose level, be de-escalated to any dose, or no future escalation may be made, even if the rule indicates “E” to escalate.
- Before MTD is reached, if PK evidence suggests the dose-exposure and TE relationship is saturated, dose escalation may be discontinued.
- The need for dose escalation to a specific dose beyond **CCI** mg QD or de-escalation to an intermediate dose level will be evaluated jointly by investigators and the sponsor based on cumulative clinical safety, PK, and preliminary efficacy data.

The stopping rules for this portion of the study are defined in Section [6.2.2](#).

PK week: The PK week is defined as 7 days prior to cycle 1 day 1 (C1D1), during which a single dose of HMPL-306 will be administered on Day 1 of PK week (Day - 7 relative to C1D1). Serial blood samples will be collected from Days 1 to 7 of the PK week for analysis of plasma concentrations of HMPL-306, 2-HG, and other biological markers as defined by the sponsor.

Study treatment: One cycle of study treatment is defined as 28 days of continuous, daily dosing. After the PK week, dose escalation will start at **CCI** mg QD orally (PO) for Cohort 1 and then escalate in the sequence of **CCI** mg QD, and **CCI** mg QD (see [Table 4](#)). The modified Fibonacci sequence will be used to increment the dose (see [Table 5](#) for details on the dose escalation decision).

No DLTs or safety concerns were noted in dose levels 1 to 3. Based on the collective results of the preclinical in vitro and in vivo safety pharmacology, at a clinical dose of **CCI** mg, the risk for potential effects on the cardiovascular, respiratory, and central nervous systems is considered low after administration of HMPL-306. The anticipated human exposure (as determined by area under the curve [AUC]) at a clinical dose of **CCI** mg QD did not result in severe toxic findings in the 4-week toxicology studies and is expected to be well below the exposures at the highest doses studied. Please refer to the most recent IB for additional information.

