6.1.10.4 Blood Chemistry

Blood chemistry will all be performed per Schedule of Events ([Table 1](#) and [Table 2](#)). This assessment should include blood urea nitrogen, creatinine, glomerular filtration rate, creatinine clearance rate; uric acid, electrolytes such as sodium, potassium, magnesium, chloride, calcium, and phosphorus, and glucose, creatine phosphokinase, and liver function tests such as total bilirubin, direct bilirubin, indirect bilirubin, ALT, AST, ALP (alkaline phosphatase), lactate dehydrogenase, total protein, and albumin.

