6.1.19 Follow-up Period

Safety Follow-up

All patients who have completed an EOT Visit will have a Safety Follow-up Visit. The Safety Follow-up Visit will be conducted at 30 days (± 7 days) from EOT Visit.

AEs related to the study drug will be followed until resolution and SAEs will be followed until resolution regardless of the relationship to the study drug.

All female patients of childbearing potential must complete a pregnancy test (serum or urine) during the Safety Follow-up Visit. Pregnancy testing should be repeated for patients with suspected pregnancy. This is not applicable for postmenopausal female patients (defined as at least 12 months of amenorrhea without alternative medical cause), and the date of menopause should be recorded instead.

Efficacy Follow-up

Patients who discontinue the study drug due to reasons other than disease progression, death, lost to follow-up, or withdrawal of consent will remain on study for tumor assessments and will be followed every 12 weeks (± 14 days) from the EOT visit or last assessment, until disease progression, initiation of new anticancer therapy, withdrawal of consent, lost to follow-up, death, conditions are met per Section [6.2.1](#), or the end of the study, whichever comes first.

Survival Follow-up

All patients will be followed for survival status every 12 weeks (± 14 days), until death, lost to follow-up, or withdrawal of consent. Survival information can be obtained via phone and information will be documented in the source documents and relevant CRFs.

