4.1.4. Treatment Period

Unless otherwise specified, the treatment period is defined as the duration from the date of the first study drug administration to 30+7 days (7-day window only replies to parameters collected by visit) after the date of last administration of study drug or prior to the start of a subsequent anti-tumor therapy (whichever comes first). For safety data, only the assessments/events collected during the treatment period will be summarized.

The worst post baseline is defined as the worst assessments/events during the treatment period including both scheduled and non-scheduled visit. Only the on-treatment safety assessments will be included in the summary tables.

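### The 14-day forward window for pairing ALT/AST with bilirubin is shorter than the gap between scheduled chemistry draws from Cycle 3, so the laboratory Hy's law row can omit delayed or reversed-order candidates

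*SAP*

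**What the plan says.** The hepatic analysis in SAP 4.4.3 has two combined categories, each with a bracketed timing rule. The first pairs ALT/AST above 3x ULN with total bilirubin above 1.5x, or at or above 2x, ULN. The second is Hy's law: ALT/AST above 3x, bilirubin at or above 2x, and "all ALP increase <2x ULN within 14 days after ALT or AST > 3x ULN". Both brackets run forward only, 14 days from the ALT/AST value. Neither says whether a bilirubin from the same sample (Day 0) counts.

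The categories "will be evaluated for any occurrence among all post baseline assessments". SAP 4.1.4 defines the worst post-baseline value as "the worst assessments/events during the treatment period including both scheduled and non-scheduled visit", so unscheduled samples are eligible. The same section limits safety summaries to the treatment period, which ends 30+7 days after the last dose or at the start of new anti-tumor therapy.

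On timing, Protocol 6.1.10.4 says "Blood chemistry will all be performed per Schedule of Events", and that panel carries ALT, AST, bilirubin and ALP together. Tables 1 and 2 place on-treatment chemistry at C1D8, D15 and D22, C2D1 and D15, then Day 1 of each later cycle, EOT and Safety Follow-up. The Synopsis agrees: "Cycle 2: every 2 weeks" (±1 day), then "Cycle 3 and onwards: day 1" (±3 days). Protocol 4.1.1 fixes the cycle: "One cycle of study treatment is defined as 28 days of continuous, daily dosing". On the last visit, Protocol 6.1.19 says "The Safety Follow-up Visit will be conducted at 30 days" (±7 days) from EOT.

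**The concern.** A pairing window can only work if samples fall inside it. From Cycle 3 the next scheduled cycle draw comes about twice as late as the window allows, and the documents schedule no repeat liver panel after an ALT/AST rise. Whether a delayed bilirubin rise is tabulated then depends on whether the site draws an extra sample or the patient happens to have an EOT visit in time.

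At stake is the one planned output that pairs the laboratory values independently of what investigators recognise and report. Protocol 2.3.1 lists hyperbilirubinemia among the most common toxicities of approved IDH inhibitors, so bilirubin timing matters here. The SAP gives no reason for the 14 days, and the protocol's own description of the liver signal in 8.1.4 has no day limit.

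**Working it through.** The plan gives no figure to reproduce. The check compares the allowed gap between consecutive scheduled draws with 14 days.

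**Inputs.** On-treatment chemistry days with C1D1 as Day 1: 8, 15, 22, 29, 43, 57, 85, 113 and so on every 28 days (Protocol Tables 1 and 2). Windows: ±1 day in Cycles 1 and 2, ±3 days from C3D1. EOT: 7 ±3 days after last dose (Protocol 6.1.18, Appendices 1 and 2). Safety Follow-up: 30 ±7 days after EOT.

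**Formula.** Gap = nominal gap + (shift of later visit) − (shift of earlier visit), taken over every allowed pair of shifts. The shares below weight all pairs equally, which is an assumption.

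| Pair | Nominal | Range (days) | Pairs within 14 days |
|---|---|---|---|
| C1D8 to C2D1, each step | 7 | 5–9 | all |
| C2D1 to C2D15 | 14 | 12–16 | 6/9 = 67% |
| C2D15 to C3D1 | 14 | 10–18 | 12/21 = 57% |
| C3D1 onward, each step | 28 | 22–34 | 0/49 = 0% |
| EOT to Safety Follow-up | 30 | 23–37 | none |

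The 22–34 range is 28 − 3 − 3 to 28 + 3 + 3. A window of 28 days reaches the next Day 1 draw in 28/49 = 57% of pairs, 30 days in 39/49 = 80%, and 34 days in all.

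**EOT as an exception.** If the last dose is *s* days after a Day 1 ALT/AST rise, EOT falls on day *s* + 4 to *s* + 10. It lies within 14 days for certain if *s* ≤ 4, nominally if *s* ≤ 7, and possibly up to *s* = 10.

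**Which patterns are lost.** Take two consecutive Day 1 visits with no sample between them. Let A mean ALT/AST > 3x and B mean bilirubin ≥ 2x, with ALP < 2x throughout. If Day 0 counts, the 14-day rule finds (A1 and B1) or (A2 and B2). A forward window of at least 34 days adds (A1 and B2). Of the 16 possible patterns, exactly one is gained: A1 yes, B1 no, A2 no, B2 yes. Pairing in both directions adds (B1 and A2), which gains one more: B1 yes, A1 no, B2 no, A2 yes. If Day 0 does not count, even a same-sample elevation from Cycle 3 needs a further sample within 14 days.

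**Share of treatment affected.** Under the six-cycle limit in Protocol 6.2.1.1, Cycles 3 to 6 are 4 × 28 = 112 of 6 × 28 = 168 days. Responders may continue beyond that.

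**Size of one omission.** The SAP summarises safety by dose level and total. Protocol 4.1.1 sets at least 3 patients per level, extendable to 12: 1/12 = 8% to 1/3 = 33%. Taking the planned 24 to 30 evaluable Part 1 patients as the total: 1/30 = 3.3% to 1/24 = 4.2%. The actual number enrolled is blacked out.

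**Treatment-period limit.** Safety Follow-up falls 4 + 23 = 27 to 10 + 37 = 47 days after last dose, nominally 7 + 30 = 37. The SAP 4.1.4 limit is 30 + 7 = 37 days. A visit at the nominal time is therefore on the limit, and a later one is outside it.

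**The case against.** The case for leaving the rule alone has real substance.

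A reader might infer that sequential cases are missed in general, or that nothing scheduled can fall in the window after about Day 57. The documents do not support either. Unscheduled samples count, an EOT visit soon after a Day 1 rise can fall inside the 14 days, and a later bilirubin rise is still found if ALT/AST remains above 3x at that visit (given Day 0 counts). For Grade 3 events at least possibly related to drug, Protocol Table 9 turns on improvement within 7 days, which implies a retest. That stands, and it narrows the loss to the patterns shown. It does not remove it, because no retest is scheduled for ALT/AST rises generally.

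A reader might also infer that DLT decisions, expedited reports or the liver AESI are compromised. They are not. DLTs are judged in C1D1–C1D28, when chemistry is weekly from D8, and the DLT-evaluable set comes from SRC decisions (SAP 3.1.3). Investigators report Hy's law within 24 hours under Protocol 8.2.2 with no 14-day condition. The hepatic AESI is found by a MedDRA query on reported events (SAP 5.2.11.2). A patient with a lost pattern still appears in the separate ALT/AST and bilirubin rows and in the listings.

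Those routes rely on recognition and reporting, however, and the separate rows do not link the two values in one patient. Protocol 8.1.4 also prints the ALT/AST trigger as below 3x ULN, whereas SAP 4.4.3 uses above 3x. The two passages must be reconciled.

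Finally, a wider two-way window will pair some unrelated abnormalities in patients with leukaemia. That is a fair cost, and it is the reason for medical review of each candidate.

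**Conclusion.** The concern holds for the laboratory table. Applied exactly, SAP 4.4.3 cannot pair a Day 1 ALT/AST rise from Cycle 3 onward with the next scheduled cycle draw (22–34 days against 14). It may also fail between C2D1 and C2D15 (up to 16 days) and between C2D15 and C3D1 (up to 18), and always fails between EOT and Safety Follow-up (23–37). It never pairs a bilirubin value that came before the ALT/AST rise. The omitted candidates are those whose two elevations never share a sample and for whom no unscheduled or EOT draw brings a qualifying bilirubin into the 14 days.

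This rests on Day 0 being counted, on visits held within their windows, and on ALP staying below 2x ULN. The documents give no basis for estimating how often the pattern will occur; it may not occur at all. If it does, one patient is visible in a small dose column. The change is inexpensive and worth making, but the gap is no threat to dose decisions or safety reporting.

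**What to change.** In both bracketed definitions of SAP 4.4.3:

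- State that same-day values count.
- Pair ALT/AST and bilirubin before or after each other within at least 34 days, or 37 days for EOT to Safety Follow-up. Pairing at any time in the treatment period is an acceptable alternative. Use this as the main definition, or as a sensitivity table beside the 14-day one.
- For Hy's law, apply the ALP < 2x ULN condition at the qualifying ALT/AST and bilirubin dates. If it stayed on every ALP in the window, a longer window would itself exclude more patients.
- State whether Safety Follow-up samples later than the 30+7-day treatment period in SAP 4.1.4 are included. Without this, a 37-day pairing window will not reliably recover that pair.
- List every candidate with dates and values for medical review.

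The cost is SAP wording, one programming parameter, one listing, and review of some false-positive pairings. No visit, sample or clinical rule changes.

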4.4.4. ECG

Electrocardiogram (ECG) parameters include heart rate, RR interval, PR interval, QT interval, QRS interval, QTcF intervals. Change from baseline to each post-baseline visit will be calculated. For the ECG triplicate assessments at a timepoint, the average of the triplicate assessment will be derived to represent the assessment at the timepoint. An overall ECG interpretation includes the following categories: Abnormal, clinically significant; Abnormal, not clinically significant; Normal; Unknown. For the ECG triplicate assessments at a timepoint, the worst interpretation will be applied for the summary.

Potentially clinically significant ECG findings will be identified using the criteria which are included in [Table 11](#).

Additionally, the minimum, and maximum values for each patient over the entire treatment period for each ECG parameter will also be derived. The change from baseline will also be calculated using these minimum and maximum values.

Table 11 Potentially Clinically Significant Criteria for ECG

ECG Parameter (unit)	Criterion value
Heart Rate (bpm)	>120
	<50
PR Interval (ms)	≥ 210
RR Interval (ms)	> 1200
	< 500
QRS Interval (ms)	≥ 120
	≤ 50
QT Interval (ms)	≥ 500
	≤ 300
QTcF (ms)	> 450
	> 480
	> 500
	≤ 300
	Increase from baseline > 30
	Increase from baseline > 60
	> 450 and increase from baseline > 30
	> 450 and increase from baseline > 60
	> 480 and increase from baseline > 30
	> 480 and increase from baseline > 60
	> 500 and increase from baseline > 30
	> 500 and increase from baseline > 60

4.4.5. Vital Signs

Vital signs include systolic blood pressure, diastolic blood pressure, respiratory rate, body temperature, heart rate, weight, Body Mass Index (BMI) will be computed as weight (kg)/[height (m)]².

For vital signs, change from baseline to each post-baseline visit and time-point will be calculated.

The potentially clinically significant findings of vital signs will also be defined based on criteria defined in [Table 12](#).

Additionally, the minimum and maximum values for each patient over the entire treatment period for each vital sign parameter will also be derived. The change from baseline will also be calculated using these minimum and maximum values.

Table 12 Potentially Clinically Significant Criteria for Vital Signs

Vital Sign Parameter	Criterion value
Systolic blood pressure (SBP) (mmHg)	≥ 160 ≥ 180 ≤ 90 ≥ 180 and an increase ≥ 20 from baseline
Diastolic blood pressure (DBP) (mmHg)	≥ 105 ≤ 50 ≥ 105 and an increase ≥ 15 from baseline
Temperature (°C)	≥ 38.5 ≤ 35.5
Pulse rate (beats/min)	≥ 120 ≤ 50

Vital signs are listed by patient and visit.

4.4.6. Performance Status

ECOG performance status is to be summarized descriptively using counts and percentages by visit. In addition to the collected ECOG score during a Cycle, the maximum post-baseline value for a patient will be derived; both scheduled and unscheduled assessments will be used to identify the maximum post-baseline values.

ECOG performance status is listed by patient and visit.

4.4.7. Echocardiogram (ECHO)

ECHOs are performed at Screening Period, on Day 1 of every treatment cycle for the first 3 cycles, every other cycle thereafter, and at EOT visit. Assessment parameters include left ventricular ejection fraction and overall interpretation of cardiac function. MUGAs are permitted if ECHOs cannot be performed.

4.4.8. Physical Examination

A comprehensive physical examination at Screening includes patient general appearance, eyes, ears, nose and throat, head and neck, respiratory, cardiovascular, abdomen (gastrointestinal), skin, mucous membranes, genitourinary system, lymph nodes, musculoskeletal, neurological, renal assessments.

Limited physical examination at scheduled visits is a subset of the comprehensive physical examination as deemed appropriate by the investigator.

Results of physical examination are listed by patient and visit.

4.4.9. Ophthalmologic Assessments

Ophthalmologic assessments, including eye appearance, slit lamp examination, best corrected visual acuity, visual field, eye movement, pupil reflex, optical coherence tomography, and intraocular pressure, will be performed during the study according to the study schedule of assessments. If the subject has undergone the relevant examinations 60 days before the start of IP treatment (C1D1), they need not be repeated. Other ophthalmic examinations are to be performed when clinically indicated. If the subject develops an ophthalmic AE related to HMPL-306, the

frequency of the examination should be increased to once every cycle until the AE is relieved or stable.

